7.2. Pharmacokinetic Concentration Analysis

Plasma concentrations of ANA001 will be summarized by cohort/dose and nominal timepoint with descriptive statistics: n, mean, SD, CV%, geometric mean, geometric CV%, median, minimum, and maximum.

Linear and semi-logarithmic plots of the mean plasma concentration by actual sampling time will be provided by cohort. For the MAD part, these plots will be done for both Day 1 and Day 7. Individual subject plots may also be provided for ANA001 in linear and semi-logarithmic plasma concentrations. Additionally, for the MAD part, plots of the trough concentrations by dosing intervals may be plotted to understand the achievement of steady state.

For each part, plasma concentrations of ANA001 at each nominal timepoint will be listed by subject.

7.3. Pharmacokinetic Parameter Analysis

The following PK parameters will be calculated:

- $AUC_{(0-t)}$
- $AUC_{(0-\text{last})}$
- $AUC_{(0-\infty)}$ (SAD only)
- C_{\max}
- t_{\max}
- $t_{1/2}$
- CL/F
- Vz/F

Actual timepoints will be used for non-compartmental analysis (NCA) calculation.

The area under the curve (AUC) is estimated using linear/log trapezoidal rule with at least three measurable concentrations. For profiles including less than three consecutive measurable timepoints or more than two embedded BLQ values, no AUC will be reported.

Analysis for the SAD Part:

For the SAD part of the study, in calculating $AUC_{0-\infty}$, the terminal elimination phase will be identified by regression analysis using logarithmically transformed plasma concentrations. An elimination phase will be considered invalid for the following situations:

- It has less than 3 data points;
- It has a positive slope (or correlation coefficient $[r] > 0$);

Adjusted $r^2 \leq 0.8$. (Adjusted $r^2 = 1 - \{(1-r^2) \times (n-1)\} / (n-2)$, where n is the number of data points in the regression and r^2 is the square of the correlation coefficient). PK parameters will be summarized using descriptive statistics (n, mean, SD, CV%, geometric mean, geometric CV%, median, minimum, and maximum) by cohort/dose. Time to maximum concentration, t_{\max} , will be summarized by n, minimum, median, and maximum only.

Dose proportionality will be assessed graphically (dose-normalized C_{\max} and AUC versus dose). If at least 3 dose groups complete the specific part of the study, dose proportionality in PK parameters may be evaluated by fitting the power model:

$$\log(C_{\max} \text{ or } AUC) = \alpha + \beta * \log(\text{dose})$$

An estimate of the slope parameter β and its 90% confidence intervals will be presented.

Individual PK parameters will be listed by subject.

Analysis for the MAD Part:

For both Day 1 and Day 7 in the MAD part of the study, PK parameters will be summarized using descriptive statistics (n, mean, SD, CV%, geometric mean, geometric CV%, median, minimum, and maximum) by cohort/dose. Time to maximum concentration, t_{\max} , will be summarized by n, minimum, median, and maximum only.

To understand drug accumulation, geometric mean ratios, and corresponding 90% confidence intervals will be calculated for Day 7/Day 1 for both AUC and Cmax.

For Day 7, dose proportionality may be assessed for steady state C_{max} and AUC using methods similar to those employed for the SAD part of the study.

8. SAFETY ANALYSIS

Safety analyses will be performed on the Safety Population. Safety endpoints include adverse events, vital signs, ECGs, physical examinations, and laboratory examinations (hematology, serum chemistry, and urinalysis).

8.1. Adverse Events

Adverse Events will be coded according to the latest version of the MedDRA dictionary.

In each part of this study, surveillance of adverse events (AE) will begin from the day the subject signs the informed consent form (ICF) until the end of the study.

Adverse events shall be recorded starting at signing of ICF. AEs will be defined as treatment-emergent adverse events (TEAE), if they occurred after initiation of study treatment or if they started prior to study drug administration but worsened after dosing, given that worsening started within the treatment period. All AEs will be listed and flagged as treatment emergent or non-treatment emergent.

Only TEAEs shall be summarized by cohort/dose in the clinical study report. Other AEs will be included in the medical history and will be listed in subject listings.

An overall summary with number and percentage of subjects with all different TEAE categories, like treatment-related, serious, and leading to discontinuation (MAD part only) provided by cohort/dose. Incidence and severity of TEAEs will be summarized by cohort/dose within System Organ Class (SOC), and within Preferred Term (PT).

TEAEs will also be summarized by relationship per SOC and PT. Relationships will be categorized into related (includes “Related” and “Possibly Related”) and unrelated (includes “Not Related” and “Unlikely Related”).

Serious TEAEs and TEAEs leading to discontinuation (MAD part only) will be summarized by cohort/dose with the number and percentage of subjects with treatment-emergent adverse events classified SOC and PT.

All AEs will be listed by subject.

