10.3.1. Safety Analyses

All safety analyses will be performed on the Safety Population. Safety parameters will include frequency of treatment-emergent AEs (TEAEs), SAEs, study drug discontinuation due to an AE (MAD portion only), concomitant medication use, and changes from baseline in clinical laboratory results, vital signs, ECG, and physical examinations. TEAEs are defined as AEs that started or worsened after dosing. Adverse events will be coded using the latest version of the Medical Dictionary for Regulatory Activities. A list of participants who have SAEs and who discontinue from the study due to an AE will be provided. Treatment-emergent AEs will be summarized by system organ class and preferred term for each dose level.

Individual results of laboratory tests (chemistry, hematology, and urinalysis) will be listed and summarized. Baseline, post-dose, and change from baseline to post-dose laboratory data will be summarized by dose. Individual results of vital signs will be listed and summarized. Observed values and changes from baseline in vital signs will be summarized by dose. Individual results of ECG parameters from the 12-lead safety ECGs will be listed and changes from baseline will be

summarized by dose. Physical examination findings and concomitant medication use will be presented in data listings.

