3. STUDY DESIGN

This is a randomized, double blind study to be conducted in two parts: single ascending dose (SAD) and multiple ascending dose (MAD).

SAD

Eligible participants will be randomly assigned to active drug (ANA001) or placebo in an 8:2 ratio. On Day 1, following an overnight fast of at least 10 hours, participants will receive their assigned treatment (1000 mg, 2000 mg, or 3000 mg of ANA001) with a standardized light meal.

A baseline ECG will be performed at Screening and at 3 hours post-dose. Blood pressure and heart rate will be measured every 8 hours while confined to the clinic. Blood for PK will be collected pre-dose and at 0.5, 1, 2, 4, 6, 8, 10, 12, and 24 hours post-dose. Participants will be discharged on Day 2 following the 24-hour PK sample and completion of clinical laboratory tests and physical examination. They will return on Day 7 (± 2) for follow-up procedures including physical examination, laboratory tests, and assessment of AEs and concomitant medication use.

SAD study design:

Cohort S1: 1000 mg (n=8) or placebo (n=2), single dose
Cohort S2: 2000 mg (n=8) or placebo (n=2), single dose
Cohort S3: 3000 mg (n=8) or placebo (n=2), single dose
Cohort S4: xx mg (n=8) or placebo (n=2) (optional; to be determined)

MAD

Eligible participants will be randomly assigned to active drug (ANA001) or placebo in a 10:2 ratio on a BID (q12h) or TID (q8h) schedule, to be determined based on the PK results of the SAD cohorts. Total daily doses are anticipated to range between 2000 mg and 4500 mg of ANA001. On Days 1 through 7, participants will receive their assigned treatment in the morning with a standardized light meal following an overnight fast of at least 10 hours. Afternoon or evening doses will be given with a light snack. A baseline ECG will be performed at Screening and at 3 hours after the second dose on Day 7. Blood pressure and heart rate will be measured every 8 hours while confined to the clinic.

During BID dosing, blood for PK will be collected on Days 1 and 7 at pre-dose and at 0.5, 1, 2, 4, 6, 8, 10, and 12 hours post-dose. Blood samples will also be collected on Days 2, 4, 6, and 8 at pre-dose and before the 12 hour dose on Days 2, 4, and 6.

During TID dosing, blood for PK will be collected on Days 1 and 7 at pre-dose and at 0.5, 1, 2, 4, 6, and 8 hours post-dose. Blood samples will also be collected on Days 2, 4, 6, and 8 at pre-dose, before the 8 hour dose on Days 2, 4, and 6, and before the 16 hour dose on Day 6.

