5.2. Key Definitions

The Study Day is the day relative to the day of study drug administration (Day 1).

Unless otherwise specified, Baseline is the last non-missing observation before the administration of study drug. The treatment period in both the SAD and MAD parts of the study is defined as Days 1-7 for subjects dosed with study drug.

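### SAP 8.1 drops worsening of a pre-dose adverse event from the TEAE count if it starts after Day 7, although the protocol sets no day limit

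*SAP*

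**What the plan says.** Protocol 10.3.1 gives a single rule with no end day: "TEAEs are defined as AEs that started or worsened after dosing".

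SAP 8.1 splits the rule in two. New events count "if they occurred after initiation of study treatment", again with no end day. Events already present before dosing count "if they started prior to study drug administration but worsened after dosing, given that worsening started within the treatment period". SAP 5.2 defines that period: "The treatment period in both the SAD and MAD parts of the study is defined as Days 1-7 for subjects dosed with study drug".

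SAP 8.1 also fixes the reporting consequence: "Only TEAEs shall be summarized by cohort/dose in the clinical study report". Of the rest it says: "Other AEs will be included in the medical history and will be listed in subject listings". It starts recording at consent: "Adverse events shall be recorded starting at signing of ICF".

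Two neighbouring rules also have date gaps:

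- **SAP 6.4.** A prior medication must start and stop before the dosing date. A concomitant one must either start before that date and be ongoing for the study, or start after it.
- **SAP 5.6.** For an event whose start date is wholly missing, the cut-off is an end date before study drug administration. For a partly missing start date, the cut-off is an end date before the start of the study, a point the SAP does not define.

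**The concern.** The SAP definition is narrower than the protocol's, and it is narrower for only one of its two kinds of event. No reason is given and it is not identified as a departure from the protocol.

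The same seven-day window also acts differently in the two parts. SAD participants are dosed on Day 1, so most of the window lies after dosing. In MAD, "On Days 1 through 7, participants will receive their assigned treatment in the morning", so the window ends on the last dosing day. A worsening first seen at the Day 8 discharge assessments is already outside it.

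TEAE incidence is a primary outcome measure (SAP 2.2.1). An event that worsened after exposure to study drug could be missing from the TEAE tables and be treated as history, while a new event of the same kind on the same day is counted.

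**Working it through.** The documents state no figure to reproduce. The check sets the definitions side by side and then counts the days on which they disagree.

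**1. Classification by case**

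| Event | Protocol 10.3.1 | SAP 8.1 with 5.2 |
|---|---|---|
| New event, Day 5 | TEAE | TEAE |
| New event, Day 10 (MAD) | TEAE | TEAE |
| Pre-dose event, worsens Day 5 | TEAE | TEAE |
| Pre-dose event, worsens Day 10 (MAD) | TEAE | not a TEAE |

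Only the last row differs.

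**2. Days left in the window after the last dosing day** (window end minus last dosing day)

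- SAD: 7 − 1 = 6
- MAD: 7 − 7 = 0

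**3. Observation days on which the definitions disagree**

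Protocol 9.2.1 collects adverse events up to the follow-up visit. If that visit is on Day F, there are F days from first dose to follow-up, and max(0, F − 7) of them fall after the cap.

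- MAD, follow-up Day 15 ± 2:
  - F = 13: 6/13 = 46%
  - F = 15: 8/15 = 53%
  - F = 17: 10/17 = 59%
- SAD, follow-up Day 7 ± 2:
  - F = 5 to 7: 0
  - F = 8: 1/8 = 12.5%
  - F = 9: 2/9 = 22%

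Days 8 and 9 are 2 of the 5 permitted SAD visit days.

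**4. Scheduled laboratory and abbreviated-examination days after the cap**

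- MAD (SAP Table 2): these assessments fall on Days 2, 5, 8 and 15 after first dose. Days 8 and 15 are beyond Day 7, so 2 of 4. As a check on the schedule, hematology at Screening, Day -1 and these four days makes 6 samples, which agrees with the blood-volume table in protocol section 9.
- SAD (SAP Table 1): post-dose laboratory tests are on Day 2 and Day 7 ± 2. That gives 0 of 2 at the nominal visit and 1 of 2 if follow-up is on Day 8 or 9.

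These counts show where a worsening could be seen and not counted. They do not estimate how many participants would be affected, and the documents give no basis for that.

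**5. SAP 6.4, with dosing date D**

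- Start < D and stop < D: prior.
- Start > D: concomitant.
- Start = D: neither.
- Start < D, stopped during the study: neither, if the ongoing condition is read literally.

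With known dates no medication meets both definitions, although the section says one can.

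**6. SAP 5.6**

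If the start of the study means first dose, the two bullets agree. If it means something earlier, such as consent, an event with an ambiguous partial start date that ended between that point and dosing is called treatment-emergent. The same event with a wholly missing start date is not.

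**The case against.** The strongest objection is that the capped rule may apply to almost nothing. Protocol 9.2.1 sends events that begin between consent and dosing to the medical history page, not the AE page. Protocol Appendix 4 makes exacerbation of a pre-existing condition an adverse event in its own right. A late worsening entered that way starts after dosing and meets the uncapped rule for new events. This stands as an argument about size. It does not rescue the wording, because SAP 8.1 records events from consent and has a rule for those that later worsen. Classification would then depend on how the site entered the event.

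Second, nothing leaves the report. All events are listed and flagged, and laboratory values and vital signs are summarized at every visit with change from baseline (SAP 8.2 and 8.3). This is true, but the primary measure is TEAE incidence, and that comes from the tables.

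Third, adverse events are collected continuously, so laboratory visit days are a poor measure of exposure. This is fair. The observation-day fractions are the better description, and neither set is an effect size.

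Fourth, protocol 10.3 calls itself a summary, so the SAP may refine it. A common end day for both kinds of event could be defended on that ground, but an unexplained limit on one kind only is harder to defend. The SAP cites the protocol dated 22 October 2020, before Amendment 1, but the amendment log shows no change to the TEAE definition, so the version gap does not appear to explain the difference.

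Fifth, the 6.4 and 5.6 points are small. This is accepted. The first changes listing flags only. The second is conditional and, where it applies, over-counts TEAEs. Some of the awkward wording in 6.4 may come from text extraction, but the dosing-date gap does not depend on it.

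**Conclusion.** The concern holds and is minor. SAP 8.1 read with 5.2 contradicts protocol 10.3.1 for pre-dose events that worsen after Day 7, and it is inconsistent with the SAP's own rule for new events. The effect lies almost wholly in MAD, where the discharge day and the entire follow-up period fall outside the window. In SAD it can arise only if follow-up is on Day 8 or 9.

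The number of affected records is probably small. It rests on an assumption the documents do not settle: whether sites record a worsening on the existing entry, where the two definitions disagree, or as a new post-dose event, where they agree. The 6.4 gap is real but confined to listing flags. The 5.6 point is an alignment of wording that matters only if the start of the study precedes first dose.

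**What to change.** - **SAP 8.1.** Delete the condition that worsening must start within the treatment period, so that any worsening after dosing counts, as in protocol 10.3.1. If the sponsor wants an end day, state one that applies equally to new and worsened events, explain it, and identify it as a departure from the protocol.
- **SAP 6.4.** Make the later-start rule *on or after* the dosing date. Make the other rule cover medications started before dosing and continued on or after the dosing date. Limit the statement that a medication can be both prior and concomitant to the missing-date cases in SAP 5.6, since no medication with known dates would meet both definitions.
- **SAP 5.6.** In the bullet on partly missing AE start dates, use study drug administration as the cut-off, as the preceding bullet does.

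The cost is a few wording edits to the SAP before database lock, with no new data, tables or procedures.

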8.2. Clinical Laboratory Assessments

All subjects in the Safety Population will be included in the presentation of the laboratory data.

Clinical laboratory parameters including hematology, biochemistry and urinalyses will be summarized by cohort/dose for each visit. In addition, changes from the baseline visit will be calculated for each visit if baseline and post-baseline measurements are available.

Shift tables may also be used to display the change from before treatment to after treatment measurement with respect to reference ranges “missing”, “low”, “normal”, “high”, and “total”.

All laboratory evaluations, including those that are unscheduled, will be listed by subject, and clinically significant values will be flagged.

8.3. Vital Signs

All subjects in the Safety Population will be included in the presentation of vital signs data.

Vital signs, including the assessments of systolic and diastolic blood pressure, pulse, oral temperature, and respiratory rate, will be summarized by cohort/dose for each visit. In addition, changes from the baseline visit will be calculated for each visit.

All assessments, including those that are unscheduled, will be listed by subject, and clinically significant values will be flagged.

8.4. ECG

All subjects in the Safety Population will be included in the presentation of ECG data.

ECG parameters, including heart rate, QT interval, QTcF interval, QTcF interval, PR interval, and RR interval, QRS interval, will be summarized by cohort/dose for each visit. In addition, changes from the baseline visit will be calculated for each visit.

All assessments, including those that are unscheduled, will be listed by subject, and clinically significant findings will be flagged.

8.5. Physical Examination

All physical examination findings, including those that are unscheduled, will be listed by subject, and clinically significant findings will be flagged.

9. ANALYSIS CONVENTIONS

Post-text tables and listings will be prepared in accordance with the current ICH Guidelines. The information and explanatory notes to be provided in the “footer” or bottom of each table and listing will include the following information:

1. Date and time of output generation;
2. Date of database lock;
3. SAS^{®1} program name, including the path that generates the output;
4. Any other output specific details that require further elaboration.

In general, tables will be formatted with a column displaying findings for all subjects. Row entries in tables are made only if data exists for at least one subject (*i.e.*, a row with all zeros will not appear). The only exception to this rule applies to tables that list the termination status of subjects (*e.g.*, reasons for not completing the study). In this case, zeros will appear for study termination reasons that no subject satisfied. The summary tables clearly indicate the number of subjects to which the data apply and unknown or not performed are distinguished from missing data.

Supportive individual Subject Data Listings will be sorted and presented by cohort, subject number, and visit date, if applicable.

Specific algorithms are discussed for imputing missing or partially missing dates, if deemed appropriate, under specific data topics. Imputed or derived data are flagged in the individual subject data listings. Imputed data will not be incorporated into any raw or primary datasets. The imputed data will be retained in the derived / analysis datasets. Imputation for missing PK data is detailed in the PK section (8.1).

The total duration for a subject *on study* will be calculated as the difference between the date of initial exposure to the study drug and the last day of observation plus one day. All calculations for defining the duration on study will follow the algorithm DURATION = [STUDY COMPLETION OR WITHDRAW DATE – FIRST DOSING DATE + 1].

This section details general conventions to be used for the statistical analyses. The following conventions will be applied to all data presentations and analyses.

- SAD and MAD will be displayed separately – all TLF titles will clearly indicate which part of the study outputs are summarizing.
- Summary statistics will consist of the number and percentage of responses in each level for categorical variables, and the sample size (n) mean, median, standard deviation (SD), minimum, and maximum values for continuous variables.
- All mean and median values will be formatted to one more decimal place than the measured value. Standard deviation values will be formatted to two more decimal places than the measured value. Minimum and maximum values will be presented with the same number of decimal places as the measured value.

- The number and percentage of responses will be presented in the form XX (XX.X%).
- All summary tables will include the analysis set sample size (i.e., number of subjects).
- Study Day 1 is defined as the first day the subject is exposed to treatment. All study days are determined relative to the day of exposure to the treatment.
- Baseline values will be defined as those values recorded closest to, but prior to, the first study treatment on Day 1.
- Change from baseline will be calculated as follows:

Change = Post-baseline value – baseline value.

- Date variables will be formatted as DD-MMM-YYYY for presentation.
- SAS® Version 9.4¹ or higher will be the statistical software package used for all data analyses.
- The study treatment, and subject number will be included in all data listings. All listings will be sorted by subject number, visit, visit date, baseline severity, etc. as applicable.

11. TABLES, LISTINGS, AND FIGURES

Tables, listings and figures will be listed in a separate Data Displays Document.
